#### 4.4 Registration Process for Other Investigative Sites

To register a participant, the following documents should be completed by the participating site and faxed to [contact] or e-mailed to [[contact]](mailto:[contact]) to the project manager:

- Signed participant consent form
- HIPAA authorization form
- Eligibility Checklist
- Cancer gene panel showing  $\geq 9$  tumor mutations per megabase
- Baseline exam note including medical/surgical history, ECOG, vital signs
- Pathology reports including documentation of HER2 status
- EKG Report
- Laboratory report including hematology, chemistries, PT/PTT, and pregnancy test
- Tumor Assessment report (CAP CT and/or MRI)
- Brain MRI report (if applicable)

To complete the registration process, the Coordinator or Project manager will follow DF/HCC Standard Operating Procedure for Human Subject Research Titled *Subject protocol Registration* (SOP #: REGIST-101) and register the participant on the protocol. The coordinator will fax or e-mail the participant study number and confirmation of registration to the participating site.

**NOTE: Registration can only be conducted during the business hours of 8:00 AM and 5:00 PM Eastern Standard Time, Monday through Friday.** Same day treatment registrations will only be accepted with prior notice and discussion with the DF/HCC Lead Institution.

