### 9. BIOMARKER, CORRELATIVE, AND SPECIAL STUDIES

In all patients in whom a tumor safely accessible, two biopsies will be required: baseline biopsy and on-treatment biopsy and at day 29 of cycle 1 (+14 day scheduling window). Optional biopsies will be performed at progression in patients who experienced an objective response during the study. We plan to use baseline biopsy tissue to perform a number of immune profiling assays, detailed below. On baseline tumor biopsies, we will perform characterization based on histology (TILs), protein expression, and mRNA expression. Additionally, we will bank specimens for possible future DNA analysis, and other further testing.

All participants will be asked to provide a sample of their archival tissue. For participants in whom tumor biopsies are not safely accessible, an archival sample will be required in order to enroll. In these cases, teams should ensure that an archival sample is available, but it does not need to be at the site in order for the patient to start treatment. Though listed as a screening procedure, archival tissue may be requested and obtained at any point throughout the trial.

Serial blood draws for correlative science are required on this trial; blood samples will be collected within 7 days before starting therapy; blood draws will be obtained every 6 weeks for 24 weeks, and then every 12 weeks, at the end-of-treatment visit in patients who are removed from treatment for progressive disease, and all efforts will be made to obtain an additional blood draw at the time of progressive disease, in patients who went off treatment for anything other than progressive disease. On each blood draw, we will perform flow cytometry to characterize protein expression of immune mediators, detailed below, and additional blood will be banked for future testing.

All patients will additionally be asked to provide a stool sample at three timepoints: within 14 days prior to starting treatment, during treatment at day 29 Cycle 1 (+14 day scheduling window), and at the end of treatment. A fourth collection may be requested from patients who experience grade  $\geq 2$  diarrhea related to study treatment after discussion with the PI. This collection is not required, but is strongly encouraged. These samples will be analyzed for microbiota content.

Sites may refer to the separate laboratory manual for additional correlative details including collection, processing, and shipping instructions.

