### 9.2.2 Collection

Biopsies will be performed at the below timepoints, if tumor is safely accessible.

Mandatory:

- Baseline (preferably after registration or on Cycle 1 Day 1 prior to dosing):
- Around C1D29 (Any time from C1D29-C2D1 is allowed)

Optional:

- At time of progression or end of treatment

For patients proceeding to the retreatment phase, optional biopsies will be performed at the below timepoints:

- C1D1 of retreatment, prior to dosing
- At the time of progression after retreatment with nivolumab

Biopsies should not be performed on Friday afternoons, as there may not be time for processing of the fresh tissue. If a biopsy must be performed on Friday morning, the lab of [name] and [name] must be notified ahead of time to ensure that there will be adequate time for processing fresh tissue, since fresh tissue cannot be stored over the weekend. The specimens in RNALater, OCT, and formalin may be stored over the weekend and shipped on Monday. Specimens in RNA Later and formalin should be stored at room temperature until shipment.

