- j. Tumor assessments should consist of 1) CT and/or MRI of the chest/abdomen/pelvis, 3) any other imaging studies (CT neck, plain films, etc.) as clinically indicated by the treating physician. The same radiographic procedures and technique must be used throughout the study for each patient (e.g., if the patient had CT chest/abdomen/pelvis performed during screening, then she should subsequently undergo CT performed using the same radiologic protocol throughout the remainder of the study). Tumor assessments will be performed at baseline, at day 1 ( $\pm 7$  day scheduling window) of Cycles 2, 3, and 4 and then every 12 week [ at day 1 ( $\pm 7$  day scheduling window) of every odd cycle: C6, C8, C10, etc.]. Additional scans are permitted as clinically indicated. All known sites of disease documented at screening should be re-assessed at each subsequent tumor evaluation.
- k. For those taken off the study for reasons other than progressive disease, tumor measurements should continue to be repeated every 6-12 weeks until first disease progression or start of a new anti-cancer therapy. Every effort should be made to maintain this scheduled, but it is understood that it may not be possible in all cases. Failure to complete scans at this interval will not be deemed protocol violations.
- l. Collected at screening, every restaging, end of treatment (if removed for progressive disease) and optionally at time of progression. See section 9.0
- m. Baseline tumor biopsy should be obtained within 28 days prior to initiating protocol therapy. On treatment biopsies should be obtained at C1D29 (+14 day scheduling window). A tumor biopsy may be performed at the end of treatment. See Section 9.2.
- n. Archival tumor sample should be collected (block or if not possible, 10-20 5micron, unstained positively charged slides). This sample may be collected at any time throughout the lifetime of the study.
- o. Baseline stool collection should be obtained within 14 days before starting protocol therapy. On treatment stool collection should be obtained at C1D29 (anytime from C1D29-C2D1). A stool collection should be obtained at the end of treatment. As these collections are for exploratory correlative purposes, failure to provide a sample at these timepoints will not constitute a protocol violation. See section 9 and/or lab manual for stool collection and processing instructions.

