Target lesions. All measurable lesions up to a maximum of 2 lesions per organ and 5 lesions in total, representative of all involved organs, should be identified as **target lesions** and recorded and measured at baseline. Target lesions should be selected on the basis of their size (lesions with the longest diameter), be representative of all involved organs, but in addition should be those that lend themselves to reproducible repeated measurements. It may be the case that, on occasion, the largest lesion does not lend itself to reproducible measurement in which circumstance the next largest lesion which can be measured reproducibly should be selected. A sum of the diameters (longest for non-nodal lesions, short axis for nodal lesions) for all target lesions will be calculated and reported as the baseline sum diameters. If lymph nodes are to be included in the sum, then only the short axis is added into the sum. The baseline sum diameters will be used as reference to further characterize any objective tumor regression in the measurable dimension of the disease.

Non-target lesions. All other lesions (or sites of disease) including any measurable lesions over and above the 5 target lesions should be identified as **non-target lesions** and should also be recorded at baseline. Measurements of these lesions are not required, but the presence, absence, or in rare cases unequivocal progression of each should be noted throughout follow up.

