## **APPENDIX B            GUIDELINES FOR COLLECTING RESEARCH BIOPSY TISSUE**

Tissue specimens will be collected from metastatic lesions using standard institutional procedures. The amount of tissue collected may follow the guidelines listed below:

*Skin/chest wall:* A goal of 2 4-mm punch biopsies will be obtained.

*Lymph node:* A goal of 3-6 core biopsy specimens will be obtained using an 18-gauge needle.

*Liver:* A goal of 3-6 core biopsy specimens will be obtained using an 18-gauge needle.

*Lung:* Because of the risk of pneumothorax associated with core needle biopsies of lung nodules, no core biopsies of lung nodules are mandated on this protocol, unless they are clinically indicated.

*Bone:* Because the yield of malignant tissue from bone biopsies tends to be relatively low, if a patient has another accessible site of disease (i.e. skin, lymph node, liver), that site should be biopsied preferentially. If bone is the only biopsy-accessible site, then a goal of 3-6 core biopsy specimens will be obtained using an 11-13 gauge needle.

**Please note that the above are guidelines for the amount of tissue to be obtained, and are not meant to replace clinical judgment at the time the procedure is performed.** Less than the goal quantity of tissue is accepted for each type of biopsy, and will be left to the clinical judgment of the physician performing the procedure.

Coded laboratory specimens will be stored in the Tumor Bank of the DFCI. These specimens will become the property of DFCI. Patients will be informed that their specimens may be used for research by investigators at DF/HCC and other approved collaborators. Shared specimens will be identified with a sample ID number; all patient identifying material will be removed.

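### Lesions sampled by the mandatory research biopsies may also be RECIST target lesions, so biopsy effects can enter the sum of diameters behind the primary ORR; the likely effect is small and its frequency unknown.

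*Combined protocol and SAP*

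**What the plan says.** **Target lesions.** Section 11.1.2 makes targets of "All measurable lesions up to a maximum of 2 lesions per organ and 5 lesions in total, representative of all involved organs". Choice among them follows size, organ representation and reproducibility of measurement: "Target lesions should be selected on the basis of their size (lesions with the longest diameter), be representative of all involved organs". Biopsy is not mentioned.

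**Biopsies.** Section 9 states: "In all patients in whom a tumor safely accessible, two biopsies will be required". Section 9.2.2 times the first as "Baseline (preferably after registration or on Cycle 1 Day 1 prior to dosing" and the second as "Around C1D29 (Any time from C1D29-C2D1 is allowed". The Study Calendar (Section 10, note m) adds: "Baseline tumor biopsy should be obtained within 28 days prior to initiating protocol therapy". For skin and chest wall, Appendix B says "A goal of 2 4-mm punch biopsies will be obtained". For node and liver it aims for 3-6 cores with an 18-gauge needle, while the Section 9 specimen table lists 5-7 cores. Appendix B presents its amounts as goals and accepts less.

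**Scans.** Baseline evaluation may be up to 4 weeks before treatment (Section 11.1.3). Sites outside DF/HCC must send the "Tumor Assessment report (CAP CT and/or MRI") in order to register a patient (Section 4.4). The first on-treatment assessment is at C2D1 ±7 days (Section 10, note j).

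**Comparable safeguards.** Palliative radiotherapy is restricted to areas that are not being followed for response (Section 5.4.1), and previously irradiated lesions do not count as measurable (Section 11.1.2). No matching rule for biopsied lesions appears in Sections 9.2, 10 or 11 or in Appendix B.

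**The concern.** The trial's own procedures can alter a lesion whose diameter feeds the primary endpoint. A patient with few lesions may have only target lesions available to biopsy, because every measurable lesion up to the cap is a target.

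The change can go either way. Tissue loss or wound contraction lowers the sum and could complete a partial response. Swelling or hematoma shortly before the C2D1 scan raises it and could complete a progression. Under Section 11.1.3.4 best response is counted only until progression, so a false progression at C2D1 forfeits any later RECIST response, even though Section 5.5 lets treatment continue under irRC.

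The four-week confirmation does not remove the first problem, since tissue taken out can still be missing at the confirming scan. There is no control arm in which the same artifact would occur.

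**Working it through.** **1. The plan's own figure, to show how few responders decide the trial.** Section 13.2 enrolls 14 patients, continues if at least 1 responds, adds 16, and calls the regimen worthy of further study at 4 or more of 30. The exact probability of success is the sum over x ≥ 1 of P(X₁ = x; 14, p) × P(X₂ ≥ 4 − x; 16, p).
- At p = 0.25 this is 0.952, in line with the stated power above 90%.
- At p = 0.05 it is 0.057, against a stated value below 5%. That mismatch is a separate matter for Section 13.2 and does not bear on biopsies.
- At p = 0.05 the chance of no response in stage 1 is 0.95¹⁴ = 0.488, so one response often decides whether stage 2 opens.

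**2. Order of events.** C1D29 to C2D1 is day 29 to day 43. C2D1 ±7 days is day 36 to day 50. At sites outside DF/HCC the scan precedes registration, and the baseline biopsy is preferred after it. Both biopsies can therefore fall between the baseline measurement and the first scan. Other orders are also allowed: the scan on day 36 could precede a biopsy on day 43.

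**3. Core biopsies** (assumed: spherical lesion of diameter D, cores spanning it, core width d of 0.8 to 1.2 mm; the documents give only the gauge). Volume fraction removed by k cores = k(π/4)d²D ÷ (π/6)D³ = 1.5kd²/D². Equivalent diameter loss = 1 − (1 − fraction)^(1/3).
- 7 cores, D = 10 mm: fraction 0.067 to 0.151, diameter loss 2% to 5%.
- 7 cores, D = 15 mm (the smallest measurable node, by short axis): fraction 0.030 to 0.067, loss 1% to 2%.
- 7 cores, D = 20 mm: fraction 0.017 to 0.038, loss about 1%.
- 14 cores over both biopsies in the same 10-mm lesion, d = 1.2 mm: fraction 0.302, loss 11%. This is the extreme.

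**4. Punch biopsies** (assumed: no healing or closure).
- *Ceiling.* A 4-mm punch cannot remove more than 4 mm of a measured axis. Partial response needs a 30% fall in the sum (Section 11.1.3.1), so one punch cannot reach it alone if the baseline sum exceeds 4/0.30 = 13.3 mm. For two punches in line the limit is 8/0.30 = 26.7 mm.
- *Round 10-mm nodule.* One punch removes at most the arc of rim with a 4-mm chord, 2·arcsin(2/5) = 47.2°. A pair removes at most 94.3° of the 180° of possible diameter directions. A full 10-mm diameter remains, so the RECIST change is 0%.
- *Elongated nodule, 10 × 4 mm (assumed shape).* Take the ellipse x²/25 + y²/4 = 1 and a punch (x − 3)² + y² = 4 at one end. They meet where 0.84x² − 6x + 9 = 0, at x = 2.14 and x = 5. The longest remaining diameter runs from (−5, 0) to (2.14, 1.81): √(7.14² + 1.81²) = 7.37 mm, a 26% loss. With one punch at each end it is 2√(2.14² + 1.81²) = 5.61 mm, a 44% loss.

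Tissue removal alone can thus reach −30% for a narrow nodule that is the only target, but not for a round one with a single pair of punches.

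**5. The other direction.** Progression needs +20% and at least +5 mm over the smallest sum. The 5-mm condition governs for sums below 5/0.20 = 25 mm, so in a small lesion swelling must reach a full 5 mm.

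**The case against.** The strongest case against is about size, and most of it stands.

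- RECIST uses the longest diameter, and punches in a round nodule leave it intact. Cores matter little, lung cores are not mandated and bone lesions are not measurable. What remains is a narrow group, and the documents do not say how many patients fall in it.
- Nothing says the largest lesion is the one biopsied. Appendix B ranks by site and safety. Nor must the same lesion be sampled twice.
- Section 11.1.2 already prefers targets that can be measured reproducibly. Section 11.1.3 prefers imaging to clinical examination and recommends photographs with a ruler for skin lesions. These reduce the problem but do not address tissue removed between measurements.

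Three stronger readings are tempting, and the documents support none of them.

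- *Lost area.* Two 4-mm punches take 2 × π × 2² = 25.1 mm², which is 32% of a 10-mm nodule (78.5 mm²) and 14% of a 15-mm one (176.7 mm²), or 64% and 28% if a second pair comes from the same nodule. A reader might infer changes of that order in the endpoint. Area is not the endpoint's metric.
- *Near misses.* The chance of finishing at exactly 3 of 30 with stage 1 passed is 11% at a true ORR of 5% and 20% at 10%. The arithmetic is correct, but it describes how often any single misclassification would be decisive, not how often biopsy creates one. The 10% rate is neither design rate, and at 25% the figure is 2.3%.
- *Inflated type I error.* One can assume that some share of non-responders is misread as responders and recompute the false-positive rate. No passage supports any particular share.

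**Conclusion.** The gap holds: the protocol permits a biopsied lesion to be a target lesion and gives no rule for handling it. It does not follow that mandatory biopsies will produce responses. The plausible effect is a few percent of diameter for cores. It can be material only for small or elongated skin or chest-wall nodules sampled by punch with little other target disease, or for patients already close to a threshold. The direction is uncertain, since swelling works against response.

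No error rate can be attached, because the documents give neither the share of patients with such disease nor the share whose target is biopsied. The size statements rest on assumed core widths, idealized lesion shapes and no healing; wound contraction could add to the loss and is not quantified. The point is worth making because a single response can open stage 2 or decide the final result in an uncontrolled trial, and the remedy costs little. It is an inexpensive improvement, not a threat to the design.

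**What to change.** 1. **Sections 11.1.2 and 9.2.2.** State that, where another measurable lesion exists, the lesion chosen for research biopsy is not used as a target lesion, or that a non-target lesion is biopsied where feasible. Word this as an exception to the rule that all measurable lesions up to the cap are targets. Site choice and safety under Appendix B stay as they are.
2. **Case report form.** Record which lesion was biopsied at each time point and the date, so that it can be set against the scan dates.
3. **Section 13.3.** Add a sensitivity analysis of ORR that leaves biopsied lesions out of the sum at both baseline and follow-up. List patients whose only target lesion was biopsied separately and count them as non-responders in that analysis. The primary analysis is unchanged.

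Do not require the baseline to be re-measured after the biopsy. Swelling could inflate the reference sum, so that its resolution would look like shrinkage. A repeat scan might also be needed at sites that submit imaging before registration, and re-measurement would do nothing about the second biopsy.

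The cost is a few lines of protocol text, a lesion identifier and date on the case report form, and one additional analysis. The downside is that some patients will have one fewer target lesion.

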### 11.1.3 Methods for Evaluation of Disease

All measurements should be taken and recorded in metric notation using a ruler, calipers, or a digital measurement tool. All baseline evaluations should be performed as closely as possible to the beginning of treatment and never more than 4 weeks before the beginning of the treatment.

The same method of assessment and the same technique should be used to characterize each identified and reported lesion at baseline and during follow-up. Imaging-based evaluation is preferred to evaluation by clinical examination unless the lesion(s) being followed cannot be imaged but are assessable by clinical exam.

Clinical lesions. Clinical lesions will only be considered measurable when they are

superficial (*e.g.*, skin nodules and palpable lymph nodes) and  $\geq 10$  mm in diameter as assessed using calipers (*e.g.*, skin nodules). In the case of skin lesions, documentation by color photography, including a ruler to estimate the size of the lesion, is recommended.

Chest x-ray. Lesions on chest x-ray are acceptable as measurable lesions when they are clearly defined and surrounded by aerated lung; however, CT is preferable.

Conventional CT and MRI. This guideline has defined measurability of lesions on CT scan based on the assumption that CT thickness is 5mm or less. If CT scans have slice thickness greater than 5 mm, the minimum size of a measurable lesion should be twice the slice thickness. MRI is also acceptable in certain situations (*e.g.* for body scans).

Use of MRI remains a complex issue. MRI has excellent contrast, spatial, and temporal resolution; however, there are many image acquisition variables involved in MRI, which greatly impact image quality, lesion conspicuity, and measurement. Furthermore, the availability of MRI is variable globally. As with CT, if an MRI is performed, the technical specifications of the scanning sequences used should be optimized for the evaluation of the type and site of disease. Furthermore, as with CT, the modality used at follow-up should be the same as was used at baseline and the lesions should be measured/assessed on the same pulse sequence. It is beyond the scope of the RECIST guidelines to prescribe specific MRI pulse sequence parameters for all scanners, body parts, and diseases. Ideally, the same type of scanner should be used and the image acquisition protocol should be followed as closely as possible to prior scans. Body scans should be performed with breath-hold scanning techniques, if possible.

FDG-PET. While FDG-PET response assessments need additional study, it is sometimes reasonable to incorporate the use of FDG-PET scanning to complement CT scanning in assessment of progression (particularly possible 'new' disease). New lesions on the basis of FDG-PET imaging can be identified according to the following algorithm:

- (a) Negative FDG-PET at baseline, with a positive FDG-PET at follow-up is a sign of PD based on a new lesion.
- (b) No FDG-PET at baseline and a positive FDG-PET at follow-up: If the positive FDG-PET at follow-up corresponds to a new site of disease confirmed by CT, this is PD. If the positive FDG-PET at follow-up is not confirmed as a new site of disease on CT, additional follow-up CT scans are needed to determine if there is truly progression occurring at that site (if so, the date of PD will be the date of the initial abnormal FDG-PET scan). If the positive FDG-PET at follow-up corresponds to a pre-existing site of disease on CT that is not progressing on the basis of the anatomic images, this is not PD.
- (c) FDG-PET may be used to upgrade a response to a CR in a manner similar to a biopsy in cases where a residual radiographic abnormality is thought to represent fibrosis or scarring. The use of FDG-PET in this circumstance should be prospectively described in the protocol and supported by disease-specific medical literature for the indication. However, it must be acknowledged that both approaches may lead to false positive CR due to limitations of FDG-PET and biopsy resolution/sensitivity.

Note: A 'positive' FDG-PET scan lesion means one which is FDG avid with an uptake greater than twice that of the surrounding tissue on the attenuation corrected image.

PET-CT. At present, the low dose or attenuation correction CT portion of a combined PET-CT is not always of optimal diagnostic CT quality for use with RECIST measurements. However, if the site can document that the CT performed as part of a PET-CT is of identical diagnostic quality to a diagnostic CT (with IV and oral contrast), then the CT portion of the PET-CT can be used for RECIST measurements and can be used interchangeably with conventional CT in accurately measuring cancer lesions over time. Note, however, that the PET portion of the CT introduces additional data which may bias an investigator if it is not routinely or serially performed.

MIBG (meta-iodobenzylguanidine). The following is recommended, to assure high quality images are obtained.

Patient preparation: Iodides, usually SSKI (saturated solution of potassium iodide), are administered to reduce thyroidal accumulation of free radioiodine, preferably beginning the day prior to injection and continuing for 3 additional days (4 days total). For infants and children, one drop t.i.d. is sufficient, for adolescents 2 drops t.i.d., and for adults 3 drops t.i.d. Participants and/or parents are asked about exposure to potential interfering agents. If none is noted, an indwelling intravenous line is established. The dose of MIBG is administered by slow intravenous injection over 90 seconds.

Images from the head to the distal lower extremities should be obtained.

I-123MIBG scintigraphy is performed to obtain both planar and tomographic images.

Planar: Anterior and posterior views from the top of the head to the proximal lower extremities are obtained for 10 minutes at 24 hours and occasionally at 48 hours following injection of 10 mCi/1.7 square meters of body surface area (~150  $\mu$ Ci/kg, maximum 10 mCi). Anterior views of the distal lower extremities are adequate. A large field of view dual head gamma camera with low energy collimators is preferred.

SPECT: Most participants receiving I-123 MIBG also undergo SPECT at 24 hours, using a single or multi-headed camera with a low energy collimator. The camera is rotated through 360 degrees, 120 projections at 25 seconds per stop. Data are reconstructed using filtered back projections with a Butterworth filter and a cut off frequency of 0.2-0.5. SPECT/CT may be performed at institutions with this capacity.

Ultrasound. Ultrasound is not useful in assessment of lesion size and should not be used as a method of measurement. Ultrasound examinations cannot be reproduced in their entirety for independent review at a later date and, because they are operator dependent, it cannot be guaranteed that the same technique and measurements will be taken from one assessment to the next. If new lesions are identified by ultrasound in the course of the study, confirmation by CT or MRI is advised. If there is concern about radiation exposure from

CT, MRI may be used instead of CT in selected instances.

Endoscopy, Laparoscopy. The utilization of these techniques for objective tumor evaluation is not advised. However, such techniques may be useful to confirm complete pathological response when biopsies are obtained or to determine relapse in trials where recurrence following complete response (CR) or surgical resection is an endpoint.

Tumor markers. Tumor markers alone cannot be used to assess response.

Cytology, Histology. These techniques can be used to differentiate between partial responses (PR) and complete responses (CR) in rare cases (*e.g.*, residual lesions in tumor types, such as germ cell tumors, where known residual benign tumors can remain).

The cytological confirmation of the neoplastic origin of any effusion that appears or worsens during treatment when the measurable tumor has met criteria for response or stable disease is mandatory to differentiate between response or stable disease (an effusion may be a side effect of the treatment) and progressive disease.

